#### **Termination of the Study:**

The Principal Investigator reserves the right to terminate the study in the interest of subject welfare. The Sponsor may terminate the study for administrative reasons.

Should the study be terminated, all documentation pertaining to the study must be returned to the Sponsor. Any actions required to assess or maintain study subject safety will continue as required, despite termination of the study by the Sponsor.

#### **Protocol Deviations:**

Deviations from the protocol will be assessed as "minor" or "major" in agreement with the Sponsor. Major deviations from the protocol may lead to the exclusion of a subject from data analysis and will be considered on a case-by-case basis.

The Investigator will not deviate from this protocol for any reason without prior written approval from the Sponsor, except in cases of medical emergencies. The Investigator may deviate from the protocol without prior approval only when the change is necessary to eliminate an apparent immediate hazard to a subject. In that event, the Investigator will notify the Sponsor immediately by phone, notify the IRB, and confirm notification to the Sponsor in writing within 5 working days after the change is implemented.

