### **Withdrawal of Subjects:**

Subjects are free to withdraw from the study at any time for any reason. Every effort will be made to determine why any subject withdraws from the study prematurely and this information will be recorded in the Clinical Study Report.

In addition, subjects may be withdrawn from the study by the Principal Investigator in consultation with the Sponsor for the following reasons:

- Adverse event
- Protocol violation
- Loss to follow-up

If a subject withdraws prematurely, all data normally collected by study completion should be collected at the time of premature discontinuation or at the scheduled discharge. All subjects who withdraw from

the study with an ongoing adverse event must be followed until the event is resolved or deemed stable. At the discretion of the PI, additional follow up visits may be done for subject safety.

Withdrawn subjects will be replaced, until 60 subjects complete the study.

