**Primary Outcome Measure:**

- Incidence of intraoperative staple line bleeding from endoscopic or laparoscopic images as measured by the provided bleeding severity scale

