### **Steps and Procedures:**

The study will include 60 total consecutive cases, randomized for stapler type: 30 with the AEON™ Endostapler and 30 with Endo GIA™ Reloads with Tri-Staple™ Technology. Surgeries will be performed by [name].

All patients will undergo the standard preoperative evaluation pathway. Patients must sign informed consent for the operation.

All firings with the AEON™ Endostapler will be done with THICK MODE for the purposes of this study and shall conform to the AEON™ Instructions for Use. All firings with the Endo GIA™ Reloads with Tri-Staple™ Technology and Ultra Universal Handle should be done according to the Endo GIA™ Instructions for Use.

To measure incidence and degree of staple line bleeding, a third-party blinded evaluator will be used. No sutures, cautery or clips shall be applied during stapling for staple line bleeding, unless required at surgeon's discretion. Following the last firing, a member of the surgical or nursing team or the research coordinator present for the case will count 10 seconds and then capture images with the laparoscope. If bleeding from the staple line requires control prior to the last firing, an additional image should be captured before applying sutures, cautery, clips, etc. Five pictures will be obtained from each case: the pylorus, distal sleeve near the distal end of the staple line, mid-sleeve at the incisura angularis, proximal sleeve and GEJ near the proximal end of the staple line. These photographs will be sent by the research coordinator to the third-party evaluator either electronically or by mail. The third-party evaluator will be blinded to the device of each case. Upon receipt of photographs, the evaluator will evaluate staple line bleeding according to a provided Bleeding Severity Scale for Laparoscope Images (Appendix A) and record results in the Bleeding Severity Evaluation Sheet (Appendix E).

At the end of each case, the surgical team will fill out the relevant sections of the Data Collection Sheet (Appendix C).

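### Open-ended exclusion from analysis, replacement of patients after stapling, and no named analysis set allow the analysed groups to differ from the randomised groups

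*Combined protocol and SAP*

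**What the plan says.** Protocol Deviations: deviations are graded minor or major "in agreement with the Sponsor", and a major one "may lead to the exclusion of a subject from data analysis and will be considered on a case-by-case basis". The section gives no definition of major, no timing relative to the bleeding scores and no masking of the decision. Its second paragraph bars the investigator from deviating without prior written sponsor approval, except in a medical emergency or to remove an immediate hazard, with notification afterwards.

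Withdrawal of Subjects: besides patients who choose to leave, "subjects may be withdrawn from the study by the Principal Investigator in consultation with the Sponsor for the following reasons": adverse event, protocol violation and loss to follow-up. For a patient who withdraws early, "all data normally collected by study completion should be collected at the time of premature discontinuation" or at scheduled discharge, and on the reason for leaving, "this information will be recorded in the Clinical Study Report". The section closes: "Withdrawn subjects will be replaced, until 60 subjects complete the study". Replacement is not limited to patients who leave before stapling.

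Timing and masking: Study Details runs participation from consent to the one-month visit. The primary outcome is "Incidence of intraoperative staple line bleeding from endoscopic or laparoscopic images". The Summary lists investigator masking as none, with a masked evaluator for the primary outcome.

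Statistics: the stated purpose is non-inferiority. The section names the t-test, the chi-square test and possible regression, but no analysis set. It leaves detailed methodology to the Clinical Study Report.

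**The concern.** Randomisation protects the comparison only if patients are analysed as they were assigned. Here two routes can change who is counted after the primary outcome has been seen: exclusion for a deviation judged major case by case, and withdrawal followed by replacement. The investigator is unmasked. The sponsor's involvement is a check, but it is not masking. The blinded evaluator scores images and is given no role in withdrawals or exclusions.

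Some of these decisions could be related to bleeding. An adverse event is a listed reason for withdrawal. One procedural requirement can be missed only by a patient who bled: "If bleeding from the staple line requires control prior to the last firing, an additional image should be captured" before control is applied.

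The aim is non-inferiority, so losing AEON patients who bled would favour the claim. In arms of 30, a few decisions move the estimate visibly. Withdrawal reasons will be reported. Without a set fixed in advance, however, a reader could not tell whether exclusions were settled before the results were known.

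**Working it through.** There is no figure in the plan to reproduce: Statistics says that no formal sample size calculation was done and that 60 was chosen for feasibility. The check has two parts.

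**1. Can a patient be removed after the primary outcome is known?** The outcome is fixed in the operating room. Withdrawal remains possible until the one-month visit, and replacement continues until 60 complete. So yes. Whether the withdrawn patient's collected data are then analysed is not stated. Exclusion for a deviation has no time limit. The written-approval rule restricts intentional deviations; it does not say who is analysed. Patients can also drop out of the primary analysis without any such decision, by withdrawing between assignment and stapling or by having no usable images.

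**2. How far could this move the result?**

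Inputs from the documents: 30 patients per arm (Steps and Procedures); a score of 1 means no bleeding (Appendix E).

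Assumptions: a bleeder is a patient scoring 2 or more; bleeding rates run from 10% to 60%, because none are given.

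One arm of 30 has x bleeders and loses one of them. The resulting rate is

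- excluded: (x − 1)/29
- replaced by a patient at the arm's own rate: (x − 1 + x/30)/30
- replaced by a non-bleeder: (x − 1)/30

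The replacement rows assume that the withdrawn patient is left out of the analysis. The last column is the opposite case, one non-bleeder excluded: x/29.

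| x of 30 | Full arm | Bleeder excluded | Replaced, own rate | Replaced, non-bleeder | Non-bleeder excluded |
|---|---|---|---|---|---|
| 3 | 10.0% | 6.9% | 7.0% | 6.7% | 10.3% |
| 6 | 20.0% | 17.2% | 17.3% | 16.7% | 20.7% |
| 12 | 40.0% | 37.9% | 38.0% | 36.7% | 41.4% |
| 18 | 60.0% | 58.6% | 58.7% | 56.7% | 62.1% |

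Losing one bleeder lowers the arm's rate by 1.3 to 3.3 points. Excluding one non-bleeder raises it by 0.3 to 2.1 points.

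Upper 95% limit for AEON minus comparator, by Newcombe's method: d + √[(u₁ − p₁)² + (p₂ − l₂)²], where d = p₁ − p₂ and l, u are the Wilson limits of each arm. For 12/30 the Wilson limits are 24.6% and 57.7%, so with 12/30 in both arms the limit is 0 + √(17.7² + 15.4²) = 23.5 points. The same formula gives:

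| AEON | Comparator | What was excluded | Upper limit (points) |
|---|---|---|---|
| 12/30 | 12/30 | nobody | 23.5 |
| 11/29 | 12/30 | 1 AEON bleeder | 21.7 |
| 10/28 | 12/30 | 2 AEON bleeders | 19.8 |
| 9/27 | 12/30 | 3 AEON bleeders | 17.7 |
| 12/29 | 12/30 | 1 AEON non-bleeder | 25.0 |
| 12/30 | 11/29 | 1 comparator bleeder | 25.4 |

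If one AEON patient is excluded for reasons unrelated to outcome, the mean rate is 0.4 × 11/29 + 0.6 × 12/29 = 40.0%, unchanged. The mean upper limit is 0.4 × 21.7 + 0.6 × 25.0 = 23.7, almost unchanged. The harm therefore depends on a link between exclusion and bleeding.

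**The case against.** The best defence is that the plan has real safeguards. Bleeding is scored by an evaluator blinded to device. Withdrawn patients' data are collected and their reasons reported. Intentional deviations need prior written sponsor approval outside emergencies and immediate hazards. All of this stands, and it narrows the room for abuse. None of it says who is analysed, and the approval rule does not reach inadvertent deviations.

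The sponsor may also say that the detail is reserved for the Clinical Study Report. That is the plan's stated handling, but a report written after the data exist cannot fix the analysis set in advance.

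The link to outcome is hypothetical, and this objection holds. A reader might infer that missing the extra image would lead to exclusion, but the documents do not say that it would be graded major. A reader might also infer that withdrawn patients are dropped from the analysis because they are replaced. That is natural but not stated, and the instruction to collect their data leaves it open.

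Finally, making the as-randomised analysis primary is not neutral in a non-inferiority study: device switches can dilute a true difference and so favour the claim. That is a fair point, and it is why the per-protocol result should appear beside it.

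**Conclusion.** The concern holds as a defect in the rules, not as evidence of bias. The plan states an exclusion rule without criteria or timing and a replacement rule that extends past the primary outcome, and its Statistics section names no analysis set. Together these permit the analysed groups to depart from the randomised ones in a way related to outcome.

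On the assumed 12/30 in each arm, one to three selective AEON exclusions lower the upper limit by 1.8 to 5.8 points (23.5 − 21.7 and 23.5 − 17.7). One comparator exclusion raises it by 1.9 (25.4 − 23.5). These figures rest on assumed rates, an assumed threshold for bleeding and an assumed number and direction of exclusions. It would go too far to conclude that the trial would wrongly declare non-inferiority: no margin is stated, so no change of conclusion can be shown. The plan should be corrected, since the change is cheap.

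**What to change.** 1. Statistics: analyse the primary outcome in every randomised patient in whom stapling began, in the assigned arm, regardless of later withdrawal or deviation, using all data collected.
2. Withdrawal of Subjects: limit replacement to patients withdrawn before stapling began. Report by arm, with reasons, those randomised but not stapled and those stapled without usable images.
3. Protocol Deviations: confine exclusions to a per-protocol analysis, with the criteria listed in advance and the exclusions fixed before bleeding scores are linked to device. Because the aim is non-inferiority, report it side by side with the as-randomised analysis.

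The cost is mainly protocol wording; the plan already asks for withdrawn patients' data. There are downsides. Device switches can dilute a true difference in the as-randomised analysis. Fewer than 60 patients may complete the one-month visit. Patients lost between assignment and stapling are disclosed, not recovered, so the set is still not strictly everyone randomised. The split may depart from 30/30, at little cost in precision: for 28/32 the standard error ratio is √(1/28 + 1/32) / √(2/30) = 1.002, a widening of 0.2%.

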#### **Risks:**

There are no additional risks to the patients participating in the study other than the known risks of the chosen procedure the sleeve gastrectomy. These known risks will be explained to the participating patients through the standard consent used for this procedure. In addition, there are no known additional risks from the use of either stapler. Both staplers are FDA approved and the surgeon-investigator of this study as well as the OR staff is very familiar with both staplers and loads. The surgeon has used both staplers and loads extensively in the past (>20 bariatric cases) and he is past the learning curve for either one.

**Statistics:**

This is an open-label study (since the patient will be blinded and the evaluation for the primary outcome will be done by a third party blinded to the stapler used). Formal sample size calculations were not performed as the purpose of the study is to demonstrate non-inferiority. The number of subjects was chosen based on feasibility and is considered sufficient to meet the study objectives.

Detailed methodology for summary and statistical analyses of the data collected in this study will be documented in the Clinical Study Report. T-test and chi-square test will be used for univariate analysis of continuous and categorical data respectively. Regression analysis may be used to identify the independent effect of several parameters on primary or secondary outcomes if there are statistically significant differences in univariate analysis.

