## **SUMMARY**

The goal of this prospective, post-market study is to measure AEON™ Endostapler performance for laparoscopic bariatric surgery against the Endo GIA™ Reloads with Tri-Staple™ Technology from Medtronic. Stapler performance will be evaluated primarily by incidence and degree of staple line bleeding from endoscopic images, evaluated by a blinded third-party. The study will include 60 total consecutive cases of individuals undergoing a planned laparoscopic sleeve gastrectomy (LSG). The LSG procedure will be performed according to institutional standard-of-care and all subjects will undergo standard preoperative evaluation as well as post-operative care. Relevant data will be collected using the Data Collection sheet which should be filled out following each procedure by a member of the surgical or nursing team.

**Enrollment:** 60 Subjects Meeting Inclusion/Exclusion Criteria

**Investigator Masking:** None (Open Label)

**Primary Outcome Evaluator Masking:** Yes (Surgeon and Device)

**Devices:** AEON™ Endostapler and Endo GIA™ Reloads with Tri-Staple™ Technology and Ultra Universal Handle

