Gastroscopy will be performed, per standard protocol, at the beginning of the case to suction all gastric contents and decompress the stomach as well at the completion of the sleeve gastrectomy. Evaluation for intraluminal bleeding will be performed at the last gastroscopy according to Appendix E. During the last gastroscopy, no suctioning of the gastric contents will be performed until evaluation for bleeding is made and pictures are obtained. The gastroscopy will be performed before any use of clipping at the staple line unless for circumstances judged by the surgeon to be medically necessary to do so before the endoscopy. These instances will also be recorded. Five pictures will be obtained from each case: the pylorus, distal sleeve near the distal end of the staple line, mid-sleeve at the incisura angularis, proximal sleeve and GEJ near the proximal end of the staple line. These photographs will also be sent to the third-party evaluator for evaluation of staple line bleeding according to a provided Bleeding Severity Scale for Endoscope Images (Appendix B). Results will be recorded in the Bleeding Severity Evaluation Sheet (Appendix E).

The determination of laparoscopic and endoscopic staple line bleeding will be based on the picture with the highest bleeding severity score for laparoscopic and endoscopic evaluation separately. Every effort will be made that all pictures prior to any suctioning of the staple line laparoscopically or endoscopically.

All typical post-operative care will continue, including immediate post-operative care prior to hospital discharge as well as the standard post-operative evaluation. A hemoglobin level will be checked at the

recovery room and at 5am on postoperative day #1 per standard protocol. This hemoglobin must be drawn from the upper extremity opposite from the one with the IV running fluids or at the same extremity with the IV running fluids but distal to the IV. For each post-operative period, a member of the surgical or nursing team will fill out the relevant sections of the Data Collection Sheet (Appendix C).

There will be no follow up study data collected after this point, however the patients will continue the standard follow up regimen per the physician's practice.

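### The stated aim is non-inferiority, but the plan sets no margin and names only tests of difference; with 30 per arm, a non-significant result is weak evidence that AEON is not worse.

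*Combined protocol and SAP*

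**What the plan says.** The Statistics section of the combined protocol and SAP makes five statements that matter here.

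- Aim and sample size: "Formal sample size calculations were not performed as the purpose of the study is to demonstrate non-inferiority".
- Adequacy: "The number of subjects was chosen based on feasibility and is considered sufficient to meet the study objectives".
- Tests: "T-test and chi-square test will be used for univariate analysis of continuous and categorical data respectively".
- Regression is optional and is used only "if there are statistically significant differences in univariate analysis".
- Everything else is deferred: "Detailed methodology for summary and statistical analyses of the data collected in this study will be documented in the Clinical Study Report".

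Steps and Procedures fixes 30 patients per stapler. The primary outcome is given as "Incidence of intraoperative staple line bleeding from endoscopic or laparoscopic images as measured by the provided bleeding severity scale". The Summary words it differently: "Stapler performance will be evaluated primarily by incidence and degree of staple line bleeding from endoscopic images". Steps and Procedures takes "the picture with the highest bleeding severity score for laparoscopic and endoscopic evaluation separately", so each patient has two worst-picture scores. Appendix E labels a score of 1 as no bleeding.

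The available text gives no margin, confidence-interval criterion, significance level, power or expected bleeding rate.

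**The concern.** A non-inferiority conclusion needs a margin and a rule that compares a confidence limit with it. The t-test and chi-square test ask whether the arms differ. If they do not reach significance, that may mean the staplers are similar or that the trial is too small to tell. The regression is triggered by a significant difference, so it does not fill the gap.

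The reasoning about size is also reversed. The non-inferiority aim is offered as grounds for having no calculation, yet whether 60 patients suffice for that aim depends on a margin. Without one, the sufficiency statement has no support.

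The trial's main conclusion is at stake. If p>0.05 is read as success, a smaller or noisier trial is more likely to succeed. Leaving the methods to the Clinical Study Report also leaves open that a margin is chosen after the data are seen, although the plan does not say this will happen.

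**Working it through.** The plan has no calculation of its own to reproduce.

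**Inputs.** From the documents: 30 per arm (Steps and Procedures), with withdrawn subjects replaced until 60 complete (Withdrawal of Subjects), so no allowance for dropout. Assumed, because the documents are silent: two-sided 0.05 (one-sided 0.025 for non-inferiority), bleeding analysed as yes/no, and true incidences from 2% to 50%.

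**1. How often chi-square misses a true excess on AEON.** Each of the 31 × 31 possible tables is weighted by two independent Binomial(30, p) probabilities. The weights of tables with uncorrected Pearson chi-square below 3.84 are summed.

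| True excess on AEON | Endo GIA rate 2% | 5% | 10% | 20% | 30% |
|---|---|---|---|---|---|
| 10 points | 68% | 74% | 81% | 86% | 88% |
| 20 points | 24% | 37% | 50% | 61% | 65% |
| 30 points | 5% | 12% | 20% | 31% | 34% |
| 40 points | 1% | 2% | 5% | 10% | 10% |

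For 20% vs 40%, exact power is 39.2%, so the miss rate is 60.8%; the normal approximation gives 60.9%. With Yates' correction or Fisher's test the miss rate is 70%. At one-sided 0.05 it is 48%.

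**2. One example.** Suppose 6/30 bleed on Endo GIA and 12/30 on AEON.

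- Chi-square = 60 × (6×18 − 12×24)² / (30×30×18×42) = 60 × 32,400 / 680,400 = 2.86, p = 0.091.
- Wilson 95% limits are 0.095 to 0.373 for 6/30 and 0.246 to 0.577 for 12/30.
- Newcombe lower limit: 0.20 − √[(0.400−0.246)² + (0.373−0.200)²] = −0.03.
- Newcombe upper limit: 0.20 + √[(0.577−0.400)² + (0.200−0.095)²] = +0.41.

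The result is non-significant but compatible with an excess of about 40 points.

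**3. What 60 patients can show if the staplers are truly equal.** The same enumeration is used. Non-inferiority is concluded when the upper Newcombe 95% limit lies below the margin.

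| True incidence, both arms | Mean CI half-width (points) | Smallest whole-point margin with 80% power | Power at a 10-point margin |
|---|---|---|---|
| 2% | 13 | 17 | 26% |
| 5% | 14 | 20 | 24% |
| 10% | 17 | 24 | 18% |
| 20% | 20 | 29 | 15% |
| 30% | 22 | 32 | 14% |
| 50% | 24 | 33 | 12% |

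The Miettinen-Nurminen interval needs 25, 30, 33 and 34 points at 10%, 20%, 30% and 50%. As a hand check, the Wald margin is (1.96 + 0.8416) × √(2p(1−p)/30). At p = 0.20 this is 2.8016 × 0.1033 = 28.9 points.

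For scale, a 10-point margin at 20% incidence would need (2.8016)² × 2 × 0.20 × 0.80 / 0.10² ≈ 252 per arm.

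**4. Degree of bleeding by t-test (58 df).** The 95% half-width is 2.002 × √(2/30) = 0.52 SD. The margin with 80% power is 0.74 SD. A true worsening of 0.5 SD is non-significant in 52% of trials (noncentral t).

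**5. Two scores per patient.** If both the laparoscopic and endoscopic scores must pass at a margin giving each 80% power, joint power is 0.80 × 0.80 = 64% if they are independent and 80% if they fully agree. If either may pass, the nominal one-sided error of 2.5% can rise to as much as 5%. The plan states neither rule.

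**The case against.** The strongest reply is that non-inferiority rests on one clause. The Summary describes the goal only as measuring AEON's performance against the comparator, and the sample size is openly based on feasibility, which is reasonable for a post-market comparison of two marketed staplers. Nothing in the plan says p>0.05 will be called non-inferiority, and naming these tests does not forbid confidence intervals. This stands in part: the misreading is an inference, and restating the aim as estimation may be the most direct repair. But the clause does state the study's purpose, and the plan gives no other rule for reaching that conclusion.

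The figures also depend on assumptions. That is fair. At Endo GIA rates of 2% to 5%, a 20-point excess is missed in only 24% to 37% of trials, and the 61% requires two-sided 0.05 without correction. The quoted Newcombe margins are slightly optimistic, because at 10% to 50% incidence the exact one-sided error there is about 2.9% to 3.4%. None of this touches the missing margin or the mismatch of tests, which hold at any rate.

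The choice between the two bleeding scores is a separable problem. It belongs here only because a non-inferiority test needs a defined comparison.

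**Conclusion.** The concern holds and must be fixed if the non-inferiority aim is kept. Followed exactly, the plan cannot support its stated conclusion unless AEON proves significantly better, and its claim that the sample is sufficient is unsupported. This follows from the text and needs no assumed rate.

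The size does depend on assumptions. At two-sided 0.05 with uncorrected chi-square, a true 20-point excess goes undetected in 50% to 65% of trials at Endo GIA rates of 10% to 50%, and in 24% to 37% at 2% to 5%. Excesses of 40 points would usually be detected. Margins reachable with 80% power run from about 17 points at 2% incidence to 33 points at 50%.

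**What to change.** Amend the Statistics section before any scores are unblinded:

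1. Analyse the primary outcome as the AEON minus Endo GIA difference in the proportion with bleeding, with a two-sided 95% Newcombe or Miettinen-Nurminen interval. A worst-picture score of 2 or more is a natural definition under Appendix E, but the plan does not yet set one.
2. Name either the laparoscopic or the endoscopic score as primary and report the other with its own interval, or state that both must pass. Align the Summary and the Primary Outcome Measure.
3. Conclude non-inferiority only if the upper limit lies below a justified margin written into the protocol.
4. If no margin can be justified at 60 patients, restate the aim as estimating the difference with a 95% interval, and say that p>0.05 will not be reported as non-inferiority.
5. Report degree of bleeding as a difference in worst-picture score with a 95% interval, as supporting evidence only.
6. Replace the sufficiency sentence with expected precision: about ±13 to ±24 points for assumed incidences of 2% to 50%, labelled as an assumption.
7. State the significance level, and fix these methods in the protocol or a dated SAP instead of the Clinical Study Report.

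The cost is protocol wording, with no extra patients or data. The sponsor gives up a more favourable claim about what 60 patients can show.

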**Secondary Outcome Measures:**

- Incidence of postoperative leakage requiring intervention through 30-day post-operative evaluation period
- Incidence of intraoperative or postoperative blood transfusion within 72 hours of surgery start time
- Hemoglobin difference between preop hemoglobin and hemoglobin on postoperative day #1 as well as difference between hemoglobin at recovery room and postoperative day #1
- Incidence of reported device-related adverse events through 30-day post-operative evaluation period
- Incidence of product malfunction during stapling
- Total hospitalization time
- Postoperative pain level per standard protocol (0-10 VAS scale completed at Recovery room, 6hrs postop and 7am at POD#1)
- Postoperative nausea presence (0-10 scale VAS completed at Recovery room, 6hrs postop and 7am at POD#1)
- Incidence of vomiting: incidence (at least one per patient) per stapler group, total episodes per group and emesis material (bloody or non-bloody)
- Correlation of number of reloads used and specimen lengths and maximum widths as measured by pathology examination
- Correlation of reload color used with observed bleeding and patient's stomach thickness by path exam
- Correlation of outcome parameters with BMI, visceral fat, gender and age
- Need for clipping the staple line prior to completion of the staple line

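### The pre-op to day-1 hemoglobin change falls under a general rule of unadjusted t-tests, although pre-op hemoglobin is collected; a pre-specified ANCOVA would usually be slightly more precise at almost no cost.

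*Combined protocol and SAP*

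**What the plan says.** Secondary Outcome Measures lists the "Hemoglobin difference between preop hemoglobin and hemoglobin on postoperative day #1". The same item adds a second contrast, the "difference between hemoglobin at recovery room and postoperative day #1".

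No method is given for hemoglobin in particular. The Statistics section has a general rule: "T-test and chi-square test will be used for univariate analysis of continuous and categorical data respectively". It continues: "Regression analysis may be used to identify the independent effect of several parameters on primary or secondary outcomes if there are statistically significant differences" in the univariate analysis. That clause names no covariates and does not mention pre-op hemoglobin. Fuller methodology is deferred to the Clinical Study Report.

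The hemoglobin row of the Data Collection Sheet (Appendix C) has entries for pre-op, recovery and day 1; only the 6-hour cell is marked not applicable. Steps and Procedures plans "60 total consecutive cases, randomized for stapler type", 30 per stapler. Under Withdrawal of Subjects, "Withdrawn subjects will be replaced, until 60 subjects complete the study".

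**The concern.** The pre-op value enters the planned comparison only by subtraction. A t-test on the change fixes the weight on the pre-op value at 1. ANCOVA estimates that weight from the data. Unless the true slope of day-1 on pre-op hemoglobin is close to 1, the fixed weight leaves avoidable variance in the arm difference.

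What is at stake is the width of one confidence interval. Hemoglobin change is an objective laboratory measure related to bleeding, in a study about staple-line bleeding whose size was set by feasibility. With 30 per arm, a gain in precision that needs no new data is worth taking.

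**Working it through.** **Inputs from the documents.** 30 per arm, 60 in total (Steps and Procedures); withdrawals replaced until 60 complete (Withdrawal of Subjects); pre-op and day-1 hemoglobin both recorded (Appendix C). There is no plan figure to reproduce: the documents give no alpha, power, hemoglobin SD or effect size for this outcome.

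**Assumptions.** Two-sided 95% intervals; all 60 patients have both values; correlation r between pre-op and day-1 hemoglobin of 0.5, 0.7, 0.8 or 0.9; ratio k of day-1 SD to pre-op SD of 0.8, 0.9, 1, 1.1 or 1.25.

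**Formulas**, with s the pre-op SD:

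- Per-patient variance of the change score: s²(1 + k² − 2rk).
- Per-patient residual variance under ANCOVA: s²k²(1 − r²), multiplied by 1 + 1/(60 − 4) = 57/56 for estimating the slope.
- 95% half-width: t × √(variance × 2/30), with t = 2.0017 on 58 df (t-test) and 2.0025 on 57 df (ANCOVA).

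**Equal SDs (k = 1).** The variance ratio reduces to (1 − r²)/(2(1 − r)) = (1 + r)/2, before the factor 57/56. For example, at r = 0.7: 0.85 × 57/56 = 0.865, and √0.865 × 2.0025/2.0017 = 0.930.

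| r | Variance ratio, ANCOVA/change | Half-width, change (SD) | Half-width, ANCOVA (SD) | Ratio of half-widths |
|---|---|---|---|---|
| 0.5 | 0.763 | 0.517 | 0.452 | 0.874 |
| 0.7 | 0.865 | 0.400 | 0.373 | 0.930 |
| 0.8 | 0.916 | 0.327 | 0.313 | 0.957 |
| 0.9 | 0.967 | 0.231 | 0.227 | 0.984 |

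**Unequal SDs.** Over the 20 combinations of k and r, the variance ratio runs from 0.582 (k = 0.8, r = 0.5) to 1.018 (k = 1.25, r = 0.8), and the half-width ratio from 0.763 to 1.009. ANCOVA has the larger variance in two of the 20: 1.017 at k = 1.1, r = 0.9 (slope rk = 0.99) and 1.018 at k = 1.25, r = 0.8 (slope 1.00). There the fixed weight of 1 is already about right, and only the cost of estimating the slope remains.

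**Simulation check.** With 100,000 null trials per r and equal SDs, the variance ratios were 0.767, 0.866, 0.919 and 0.968. Type I error was 4.9 to 5.1% for both tests. The ANCOVA interval was the narrower one in 99, 94, 85 and 64% of trials, so at r = 0.8 and 0.9 it was the wider one in about 15 and 36%.

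**The same loss seen within one trial.** The chance difference in mean pre-op hemoglobin has standard error √(2/30) = 0.258 SD, so it reaches 0.25 SD or more in about 33% of trials. Given an imbalance d, the expected change-score difference shifts by (rk − 1)d. With k = 1 and d = 0.25 the size of the shift is 0.125, 0.075, 0.050 and 0.025 SD, or 0.48, 0.38, 0.31 and 0.22 of the standard error √(2(1 − r) × 2/30). ANCOVA removes this shift. The t-test's interval already allows for this variation, so these figures are not an additional harm.

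**The case against.** The strongest reply is that this is a preference. The outcome is defined as a difference, and a t-test on that difference is a legitimate and valid analysis. It is one contrast within one of 13 secondary outcome items. The gain rests on a correlation and SDs that the documents do not give. At r = 0.8 to 0.9 the interval narrows by only 2 to 4%, and in a sizeable minority of single trials it would be wider. All of this stands and limits the weight of the point. It does not remove it: within the assumed range the average loss is at most about 1% in interval width, against a gain of up to 24%.

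A second reply is that the Statistics section is only an outline. The hemoglobin t-test is indeed inferred from a general rule. But the Clinical Study Report is the reporting document, so deferring methodology to it does not pre-specify an adjustment.

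A reader might also infer that the regression clause allows adjustment of the arm comparison only after the unadjusted test succeeds. The documents do not establish this, because the clause does not say which differences must be significant. The listed "Correlation of outcome parameters with BMI, visceral fat, gender and age" makes exploratory modelling of patient factors the likelier meaning. Under either reading no baseline-adjusted arm comparison is pre-specified. The ambiguity gives no reason to relabel regression on other outcomes, including the primary one, as exploratory.

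**Conclusion.** The point holds as a small, nearly free gain in precision on one secondary outcome. With equal SDs and 30 per arm with both values, the 95% interval would on average be about 13, 7, 4 or 2% narrower at r = 0.5, 0.7, 0.8 or 0.9. Over the assumed SD ratios the range is 24% narrower to 1% wider. Those are averages, and one trial can do worse.

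A reader might go further and call the planned test biased or invalid, particularly after seeing the chance-imbalance figures. The documents do not support that. Allocation is randomized, both analyses target the same arm effect, and both hold their type I error in simulation. No conclusion of the trial is shown to change.

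Replacing withdrawn patients does not guarantee 60 complete hemoglobin pairs, and Protocol Deviations allows case-by-case exclusion from analysis. Modest losses would alter these percentages little.

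**What to change.** Add one sentence to the Statistics section, or to a separate analysis plan, before any outcome is compared by arm:

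> Day-1 hemoglobin will be compared between arms by ANCOVA with arm and pre-op hemoglobin, reported as an adjusted difference with 95% CI, whatever the univariate p-value.

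Regressing the change on the same two terms gives the same arm effect, so the listed outcome is unchanged. At most, add that the conditional regression clause does not govern this one comparison; leave its use for other outcomes as it is.

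Do not adjust the recovery-room to day-1 difference for the recovery-room value. Post-operative hemoglobin is drawn at the "recovery room and at 5am on postoperative day #1 per standard protocol", so the recovery-room sample comes after stapling and is not a baseline.

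The cost is one degree of freedom (58 to 57), with no extra patients, visits or blood draws.
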